3.0 Intervention to be studied

Emerging evidence suggests that resistance training is effective at reducing depressive symptoms.^{11,12,27} We developed an innovative rehabilitation approach, Post-stroke Optimization of Walking using Explosive Resistance (POWER) training; a high-velocity, high-intensity lower extremity resistance training intervention that improves post-stroke muscular and locomotor function (RR&D RX000844).¹³ Preliminary findings from this study suggest POWER training reduces symptoms in those with mild to moderate depression (Figure 1). We seek to build upon these findings to determine its efficacy (vs. control) in treating PSD.

Chronic stroke survivors with mild to moderate depression (n=32) will be randomly assigned to the intervention (POWER) or attention control (stretching) group. POWER training will take place over a 12-week period (3 sessions/week) with exercises including leg press, calf raises, and jump training, all performed at high concentric velocity, as well as trials of fast walking. We will perform bi-weekly measurements of depressive severity using the Hamilton Rating Scale for Depression (HRSD).

Chronic stroke survivors with mild to moderate depression (n=16) as well as age (± 5 yrs), gender and severity-matched (determined by walking speed) non-depressed stroke subjects (n=16) will complete 12 weeks of POWER training. We will perform bi-weekly HRSD measurements as well as comprehensive dynamometric assessments of paretic and non-paretic knee extensor muscle power generation and self-selected walking speed at these same time points. Secondary assessments of locomotor function will be the six-minute walk test (6MWT) and the amount of community walking measured via step activity monitors (SAM).

Stretching is being used as an attention control condition for POWER training. Control subjects will participate in a stretching protocol for the same duration (i.e. 60 minutes per session) and frequency (3 days per week) for 12 weeks to ensure that they have equal interaction with the study staff and controlling for the effects of repeated social interaction on depressive symptoms.

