Following RMT assessment, we will assess the participant's $\text{SI}_{1\text{mV}}$. The same 'hotspot' location and SA-PEST procedure will be used to determine the participant's $\text{SI}_{1\text{mV}}$, however the SA-PEST program will be set to search for MEP amplitudes of approximately 1-mV. Once established, the $\text{SI}_{1\text{mV}}$ will be used as a primary measure of corticospinal excitability. Using the %MSO of the $\text{SI}_{1\text{mV}}$ we will then collect 20 test MEP's at a rate of 0.25Hz. Once MEP's are collected, participants will be set-up for peripheral nerve stimulation. Stimulation of the median nerve of the non-dominant arm will be delivered via constant current stimulator (DS7A; Digitimer, Hertfordshire, UK). Bipolar electrodes will deliver a $200\mu\text{s}$ square wave pulse at an intensity equal to 300% sensory perceptual threshold. Perceptual threshold will be determined each session and will be defined before any stimulation protocols are commenced. Single pulse TMS will be applied to the APB muscle representation on the contralateral motor cortex 25ms (ISI25) after the delivery of median nerve stimulation. A train/delay generator (Digitimer, Hertfordshire, UK) will trigger paired peripheral nerve stimulation and brain stimulation. A total of 200 paired stimuli will be delivered at rate of 0.25 Hz, resulting in a total stimulation time of ~14 minutes. The 20 test MEP's will be reassessed immediately after PAS, and then every 15 minutes for one hour.

We will utilize the PAS measures at baseline, after 2,4,6,8,10 and 12 weeks of treatment (or control) as well as at the follow-up time point to assess whether the interventions change PAS measured neuroplastic potential. We will use PAS to assess cortical excitability ($\text{SI}_{1\text{mV}}$) as well as neuroplastic potential (represented by mean normalized post-stimulation MEP amplitude). We will compare PAS measures at baseline to after either POWER or control. We will also compare repeated PAS measures in patients with and without PSD (Aim 2) to determine whether PSD inhibits neuroplasticity, and if effective treatments reverse the impaired potential for plasticity.

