Fatigue is defined as either voluntary exhaustion or inability to maintain a minimum cycling cadence of 40 RPM. Clinical criteria for termination include: 1) Hypertension: $\geq 220/120$ mmHg, or 2) Hypotension: a drop in diastolic blood pressure >20 mmHg, and O2 saturation $<85\%$. Electrocardiogram criteria include: 1) ≥ 1 mm horizontal or down sloping ST segment depression, 2) sustained paroxysmal ventricular tachycardia (>30 beats), and 3) sustained paroxysmal supraventricular tachycardia (>30 beats). If the test is terminated because of electrocardiographic findings, the subject will be managed medically as needed, referred for care, and disapproved for participation. Resting blood pressure and heart rate will be obtained prior to initiation of exercise as well as after the subject has been sitting on the stationary bicycle for 1 minute. During the exercise test, blood pressure readings will be obtained every 3 minutes. Heart rate will be obtained from the 12-lead EKG. Maximal heart rate will be recorded as the highest heart rate achieved during the exercise tolerance test.

Subject monitoring during testing and training: Blood pressure (BP) and heart rate (HR) will be monitored prior to, during, and at completion of each session. Subjects' resting diastolic BP must be <100 mmHg, systolic < 200 mmHg, and heart rate <110 beats/min to begin the testing.⁷⁴ Criteria for termination include subject complaints of shortness of breath, light-headedness, confusion, severe headache, or dyspnea; onset of angina; excessive blood pressure (systolic BP > 200 mm Hg, diastolic BP > 110 mm Hg), or drop in systolic BP > 10 mm Hg and inappropriate bradycardia (drop in heart rate > 15 bpm).

Experimental protocol for walking data collection: At the beginning of the first training session of every other week (bi-weekly), subjects will walk on a 10m. long gait mat (GaitRite) to measure self-selected and fastest comfortable walking speed and other spatiotemporal parameters. Subjects will be permitted a practice trial, and then be asked to complete three trials at each speed. For all trials, subjects will wear their own shoes and be asked to walk without an assistive device or ankle-foot orthosis. A safety harness mounted to the ceiling will protect the subject but will only support their body weight in the case of a loss of balance. A physical therapist will be present for all testing sessions as needed.

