Post-stroke Optimization of Walking using Explosive Resistance (POWER) training: Individuals with chronic post-stroke hemiparesis will undergo training to improve muscle power generation for 12 weeks (3 times/week) that includes both resistive and task-specific elements. Session duration will be ~ 60 minutes (inclusive of rest intervals) although the total time will depend on the amount of rest needed for a given individual. Training will include five distinct resistance activities aimed at improving muscle power-- each previously reported to contribute to improved walking (Table 1). Sit to stand and leg press exercises are elements of programs shown to be effective in improving strength and walking performance in the post- stroke population.⁴⁸ Repeated step-up training using a single riser targets both eccentric and concentric training in both the sagittal and frontal planes. As possible for individual subjects, we will utilize a step height higher than standard community steps (10") to further challenge neuromuscular requirements of the task. Calf raises (i.e. plantar flexion) will be performed on a small step so as to allow for adequate range of motion. In addition, our pilot data demonstrate that jump training, focused on lower extremity muscle power generation, is part of a comprehensive program that improves gait speed in people with post-stroke gait deficits. Sit to stand, step-up and calf raise activities will be performed within the novel overground body-weight support (BWS) environment enabled by the Zero-G (ZeroG, Bioness Inc., Valencia, CA), whether receiving support or not, to provide the maximum safety possible.

During the initial training session, subjects will perform the individual component tasks beginning with least amount of BWS (or highest load) required for successful completion of

the required number of repetitions in order to match the participant's ability to the difficulty of the task.⁴⁹ BWS will be progressively reduced to determine the minimum support necessary to complete each task. Participants will be progressed within each task by decreasing BWS by 5% of body mass (or adding 5% load for leg press) upon successfully meeting the goals for progression (see Table 1). An adjustable weighted vest will be utilized to increase mass by 5% during training once support is not required for successful task completion. Subjects will not be permitted to use assistive devices and physical assistance will not be provided during training.

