
*** To provide the best care possible, those initially randomized to the control group will be offered the opportunity to re-enroll into POWER training should they still meet criteria for depression at the follow-up time point.

Dynamometric Assessment: Isometric and isotonic assessments will be performed for knee extension and ankle plantar flexion at bi-weekly intervals throughout POWER using a

Biodex isokinetic dynamometer (Biodex Corp., Shirley, NY). Prior to testing, each subject will go through a period of familiarization and warm-up consisting of 5 minutes of cycling and three sub-maximal contractions. During isometric testing, maximum voluntary isometric contraction (MVIC) will be defined as the highest torque achieved during 3 maximal contractions (~3 sec contractions separated by a minimum of 60 seconds rest). If MVIC values during the three trials differ by more than 5%, additional contractions will be performed. During isotonic testing, peak power will be assessed using 40% of MVIC. Differences in lower extremity maximal velocity are shown to occur at relatively low external forces (e.g. 40% 1 RM) and are most closely associated with gait velocity in older individuals.⁵¹ To optimize reliability of the testing, each test will be repeated 3 times. If the coefficient of variation among the 3 highest powers is > 10%, additional contractions will be performed. Power-angle curves will be plotted and the peak powers recorded. During all dynamometric testing, subjects will be instructed to (1) develop torque as fast as possible and (2) produce a maximal contraction. Subjects will be given an auditory cue and receive continuous visual feedback. All contractions will be performed with subjects positioned in the dynamometer and the axis of the dynamometer aligned with the joint axis of rotation. Proximal stabilization will be achieved with straps at the chest, hips, and knee as appropriate. In order to increase sensitivity, the force transducer signal will be amplified and fed into a data acquisition unit (Lab View Inc.) and corrected for the effects of gravity.

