12.0 Data Management

Data Analysis Plan: We will compare the effects of POWER training (vs. control) on HRSD scores. We will also determine response ($\geq 50\%$ reduction in symptoms) and remission ($\text{HRSD} < 10$) rates following training and at a six-month follow-up. We will utilize repeated measures mixed effects models to assess significant changes in outcomes between groups. Time and group will serve as dependent variables, as well as their interactions. A random intercept term will be included in the model to account for clustering within subjects. Various error structures associated with the repeated measures will be considered (e.g. compound symmetry vs. auto-regressive).

We will determine if PSD limits response to treatment by making between group comparisons of change (post-pre) in outcomes in depressed vs. non-depressed subjects utilizing repeated measures mixed models. Time (seven occasions), group (depressed vs. non-depressed) and their interaction will serve as dependent variables. Three primary dependent variables of interest here are, self-selected walking speed (SSWS) and paretic leg power generation. A random intercept term will be included in the model to account for clustering within subjects. Various error structures associated with the repeated measures over time will be considered (e.g. compound symmetry vs. auto-regressive). Analyses incorporating differences in outcomes as dependent variables will examine whether changes over time are more pronounced in depressed versus non-depressed subjects as well as whether changes are more pronounced in depressed subjects with the greatest improvement in HRSD. These models will also incorporate random subject effects to account for within-subject dependence. To determine associations between changes in outcomes, we will look at the relationships between outcomes using Pearson or Spearman correlations, depending on the distribution of the data. Further, we will use segmented (joint-point) regression to estimate if specific thresholds exist that mark in individual subjects where HRSD starts improving (decreases) and other outcomes start to improve (increase) to help us understand

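### The walking-speed testing rule gives six tests and none after the last training session, which conflicts with the seven-occasion, post-minus-pre analysis planned for Aim 2

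*Combined protocol and SAP*

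**What the plan says.** Five places bear on when walking speed is measured.

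- Section 10.0, Experimental protocol for walking data collection, gives the only operational rule: "At the beginning of the first training session of every other week (bi-weekly), subjects will walk on a 10m. long gait mat (GaitRite". It names no separate baseline or end-of-training walk.
- Section 10.0, POWER training, sets the course length: "for 12 weeks (3 times/week) that includes both resistive and task-specific elements".
- Section 12.0, Data Analysis Plan, plans "between group comparisons of change (post-pre) in outcomes in depressed vs. non-depressed subjects" and specifies "Time (seven occasions), group (depressed vs. non-depressed) and their interaction will serve as dependent variables". Walking speed is one of the variables it names as primary for this aim: "Three primary dependent variables of interest here are, self-selected walking speed (SSWS) and paretic leg power generation".
- Section 3.0 gives a second statement of timing. After providing for bi-weekly HRSD, it adds knee extensor power and "self-selected walking speed at these same time points". Section 4.0 takes the HRSD change from baseline to week 12.
- Section 10.0, on paired associative stimulation (PAS), has the only schedule written out in full: "We will utilize the PAS measures at baseline, after 2,4,6,8,10 and 12 weeks of treatment (or control", plus a follow-up point. It applies to PAS alone.

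For dynamometry, section 10.0 says "Isometric and isotonic assessments will be performed for knee extension and ankle plantar flexion at bi-weekly intervals throughout POWER", with no rule tying the test to a particular session.

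**The concern.** A test tied to the start of a training session cannot follow the last session. Staff who work from the procedure section would take their final walking-speed value before training ends, while the analysis section expects a post-training value and one more occasion than the rule supplies.

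Aim 2 asks about the rate and the extent of response. If the last value comes early, the extent is cut short. The planned correlations of change might set a 12-week HRSD change against a walking-speed change over a shorter period. The segmented regression, which looks for the earliest time of maximum effect, could not detect a late maximum in walking speed. An end-of-training walk that was not done cannot be recovered afterwards.

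**Working it through.** **Inputs.** 12 weeks and 3 sessions per week (section 10.0); seven occasions (section 12.0, Data Analysis Plan); a minimum detectable difference of 0.13 m/s (section 12.0, Sample size determination); a pilot gain in self-selected speed from 0.71 to 0.92 m/s over 24 sessions (section 2.0, Preliminary Studies).

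**The plan's figure of seven.** Baseline plus weeks 2, 4, 6, 8, 10 and 12 is 1 + 6 = 7. The PAS schedule without its follow-up point therefore reproduces the seven occasions.

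**What the walking rule gives.** Total sessions are 12 × 3 = 36. The first session of week w is number 3(w − 1) + 1, so 3(w − 1) sessions are complete when the test is done.

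| Reading | Weeks tested | Sessions completed at each test | Tests | Sessions left after last test |
|---|---|---|---|---|
| Odd weeks | 1, 3, 5, 7, 9, 11 | 0, 6, 12, 18, 24, 30 | 6 | 6 |
| Even weeks | 2, 4, 6, 8, 10, 12 | 3, 9, 15, 21, 27, 33 | 6 | 3 |

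Each reading spans 30 sessions, and 30/36 = 0.833. Neither yields seven tests or a test after session 36. The last value falls after 10 full weeks (odd) or 11 (even). The sample-size paragraph assumes 10 measurements per person, which matches neither six nor seven.

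**Gain missed, odd-week reading.** The documents give no time course of gain, so this is a range under stated assumptions.

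- Plateau by session 24: nothing is gained after session 30, so the missed amount is 0.
- Pilot rate sustained to session 36: (0.92 − 0.71)/24 = 0.00875 m/s per session, and 6 × 0.00875 = 0.0525, about 0.053 m/s.

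**Group difference, odd-week reading.** If the difference between depressed and non-depressed participants grows linearly with sessions and reaches 0.13 m/s at session 36, the last test would show 0.13 × 30/36 = 0.108 m/s.

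**With one test added after session 36** to the odd-week rule, the tests fall at 0, 6, 12, 18, 24, 30 and 36 sessions completed. That is seven occasions covering the whole course.

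**The case against.** The strongest reply is that the walking paragraph should not be read alone. It does not say that these are the only tests. Section 3.0 puts walking speed at the HRSD time points, section 4.0 carries HRSD to week 12, section 12.0 asks for seven occasions and a post-minus-pre change, and the PAS schedule shows what a seven-occasion schedule looks like. Together these point to an intended week-12 walk.

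That stands as a reading of intent, and it rules out two stronger conclusions that a reader might draw.

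- A reader might infer that walking speed has no post-training value at all. The documents do not support that: a week-12 value is implied, although no section states it.
- A reader might infer that the Aim 2 analysis cannot be run. That is also too strong. Group, time and their interaction can be estimated in a mixed model with six occasions. Both Aim 2 groups receive POWER training on the same schedule, so the contrast would still be like with like, at an earlier endpoint.

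Three further limits also stand. A pre-training speed must exist even on the even-week reading, because eligibility and matching both use walking speed, although the plan does not name that value as an outcome measurement. The mismatch with the week-12 HRSD change arises only if the walking rule is followed literally, since section 3.0 aligns the two measures. The dynamometry wording does not exclude a week-12 test, so its timing is unspecified rather than contradictory.

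The conflict itself remains. The implied week-12 walk rests on inference: section 3.0 says only bi-weekly, and the section 4.0 sentence names AET+rTMS and AET+sham groups, which are not this trial's arms. Adding the eligibility speed to the six even-week tests would bring the count to seven, but would still leave no value after session 36.

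**Conclusion.** This is an internal inconsistency that should be fixed. The only operational rule for walking speed gives six tests on either choice of weeks and none after session 36. The analysis plan calls for seven occasions and a post-minus-pre change in this primary Aim 2 variable, and section 3.0 aligns it with HRSD. A site following the rule to the letter would end the extent-of-response contrast at about 10 to 11 weeks.

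The count of six is plain arithmetic and needs no assumption beyond 36 sessions given as planned. The size of the loss does rest on assumptions. On the odd-week reading it lies between 0 and about 0.053 m/s of gain, depending on whether improvement plateaus by session 24 or continues at the pilot rate. The 0.108 m/s figure holds only if the group difference grows linearly, and the plan's own segmented regression allows for a plateau or a change of direction. The matter affects Aim 2 only; the HRSD primary outcome is not touched.

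**What to change.** Reword the walking-data paragraph in section 10.0 so that self-selected and fastest comfortable walking speed are measured before session 1 and after 2, 4, 6, 8, 10 and 12 weeks of training. State that the last test follows session 36 and takes place at the week-12 assessment already planned for PAS and HRSD. This supplies the seven occasions in section 12.0 and agrees with section 3.0. For consistency, give the same time points in the dynamometry paragraph.

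The cost is the protocol wording, one short gait-mat test at week 12, and a dynamometry test there if none was already intended. The downside is a few more minutes of testing for participants at that assessment.

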11.0 Specimen Collection and Banking

N/A

12.0 Data Management

Data Analysis Plan: We will compare the effects of POWER training (vs. control) on HRSD scores. We will also determine response ($\geq 50\%$ reduction in symptoms) and remission ($\text{HRSD} < 10$) rates following training and at a six-month follow-up. We will utilize repeated measures mixed effects models to assess significant changes in outcomes between groups. Time and group will serve as dependent variables, as well as their interactions. A random intercept term will be included in the model to account for clustering within subjects. Various error structures associated with the repeated measures will be considered (e.g. compound symmetry vs. auto-regressive).

We will determine if PSD limits response to treatment by making between group comparisons of change (post-pre) in outcomes in depressed vs. non-depressed subjects utilizing repeated measures mixed models. Time (seven occasions), group (depressed vs. non-depressed) and their interaction will serve as dependent variables. Three primary dependent variables of interest here are, self-selected walking speed (SSWS) and paretic leg power generation. A random intercept term will be included in the model to account for clustering within subjects. Various error structures associated with the repeated measures over time will be considered (e.g. compound symmetry vs. auto-regressive). Analyses incorporating differences in outcomes as dependent variables will examine whether changes over time are more pronounced in depressed versus non-depressed subjects as well as whether changes are more pronounced in depressed subjects with the greatest improvement in HRSD. These models will also incorporate random subject effects to account for within-subject dependence. To determine associations between changes in outcomes, we will look at the relationships between outcomes using Pearson or Spearman correlations, depending on the distribution of the data. Further, we will use segmented (joint-point) regression to estimate if specific thresholds exist that mark in individual subjects where HRSD starts improving (decreases) and other outcomes start to improve (increase) to help us understand

if there is a critical point of change in HRSD that is important for facilitating functional improvements. The purpose of using the segmented regression is to see if HRSD scores either plateau or change direction at a given point. The segmented regression model will essentially fit two linear models that have different slopes and intercepts but meet at a point of time. This will be achieved through inclusion of a dummy variable and its interaction with time in the model. The dummy variable will take the value 0 for time points below the threshold and 1 above. The threshold, namely the time, at which the model changes direction will be assumed unknown. Therefore, this model will be a non-linear regression model. We have written a macro in SAS to fit such models. This macro also allows for higher-order polynomials. Our intention is to fit random effects models, calling PROC NLMIXED in our macro. Other covariates can also be included in this approach. The purpose of the segmented regression model is to identify the earliest time at which there is maximum effect.

All efforts will be taken to minimize dropouts. If dropouts occur, we will attempt to determine the reason for dropout. If the dropouts occur at random, the mixed effects model can account for the missing data. However, if the dropouts are found to be treatment related, they will be treated as non-ignorable missing data and appropriate missing data methods will be applied and multiple imputations considered.

Sample size determination and Statistical Approach: A total of 50 post-stroke subjects will be recruited. For Aim 1, 32 subjects with PSD will participate in either POWER training or control intervention (n=16 per group). These analyses will rely on longitudinal measures and we assume (based on experience with this intervention) that no more than 15% will fail to complete all assessments. This is an extremely conservative approach in that none of the subjects in our pilot trial withdrew from treatment. With 16 subjects enrolled per group and a 15% attrition rate over time (resulting in complete data on 13 subjects per group), we would have at least 80% power to detect a minimum difference in the change in HRSD from baseline to the end of the study of 2.94 (change in pilot data = 6.6) with a s.d. of 5.3 (at 5% significance level). Since this is a longitudinal study, we also incorporated an autocorrelation (AR(1)) of 0.5 for 10 measurements within individuals. The published studies report treatment effect sizes ranging from 0.6 to 0.9, which are more conservative. In our preliminary data, we observed an effect size of 1.19 (95% CI 0.98 to 1.36) for improvement in depression severity. To detect this effect we will have more than 90% power. For Aim 2, with baseline data from n=26 subjects, we will have 80% power to detect a minimum difference (pre-post) of 0.13 m/s for SSWS (s.d. = 0.2 m/s) and 17.88 ft/lb for muscle strength (s.d.=31.9 ft/lb) using a longitudinal approach with an autocorrelation (AR (1)) of 0.5 for 10 measurements within individuals. In the statistical analysis for both aims, we will summarize the longitudinal data using Spaghetti plots. If the spaghetti plots suggest linear or quadratic trend we will include these in the model along with appropriate interactions and random effects. We will perform appropriate model diagnostics and, if needed, consider transformations to achieve normality. To reduce potential heterogeneity in the data, secondary analysis will adjust for covariates such as depression level.

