1.0 Objectives / Specific Aims

The purpose of this project is to determine the efficacy of POWER training for treating post-stroke depressive symptoms. We will also determine if depression limits response to rehabilitation and the extent to which changes in depression are associated with improvements in functional performance post-stroke. The PI and Co-I's have experience performing all of the proposed methodologies. Specifically, we have extensive experience implementing exercise programs in persons post-stroke;^{13,31,32,36} performing assessments of post-stroke walking;^{13,36} and diagnosing and treating depression.^{37,38,39,40}

Aim 1: Determine the efficacy of POWER training for treating PSD

We hypothesize significant reductions in HRSD scores in both groups, with improvements following POWER greater than control. We also expect greater response and remission rates in the POWER group.

Aim 2: Determine the influence of PSD on the rate and extent of response to POWER training

We posit that POWER training-induced improvements will be attenuated, though still significant, in depressed subjects. In addition, we hypothesize that improvements in walking speed and lower extremity muscle power generation will be contingent upon improvements in HRSD and that a critical threshold will determine the point at which depression is reduced thereby facilitating functional improvements.

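### Aim 2 asks whether a depression threshold exists, but the segmented regression has no no-threshold comparator, no decision rule and no interval for the break

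*Combined protocol and SAP*

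**What the plan says.** Section 1.0 makes the threshold part of the Aim 2 hypothesis: "a critical threshold will determine the point at which depression is reduced", after which function is expected to improve.

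Section 12.0 (Data Analysis Plan) gives the question to segmented regression, to be used "to estimate if specific thresholds exist that mark in individual subjects where HRSD starts improving (decreases" and where the other outcomes begin to rise. The model will "fit two linear models that have different slopes and intercepts but meet at a point of time". On the break itself: "The threshold, namely the time, at which the model changes direction will be assumed unknown". On fitting: "Our intention is to fit random effects models, calling PROC NLMIXED in our macro".

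Two sentences in section 12.0 come near to an alternative without a break. One concerns the software: "This macro also allows for higher-order polynomials". The other, in the sample size paragraph, concerns the longitudinal models for both aims: "If the spaghetti plots suggest linear or quadratic trend we will include these in the model". Neither is set against the segmented fit. The section names no test of the slope change, no information criterion and no interval for the break time. It also gives the analysis estimation purposes: to see whether scores level off or reverse, and to find how early the effect peaks.

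**The concern.** A two-line model with a free break always yields a break time. Without a model that has no break, and a rule for choosing between them, the analysis cannot answer whether a threshold exists, and this part of Aim 2 has no stated way to fail.

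Two separate errors are possible.

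- **Straight decline.** With no slope change the break time is not identified. A test that searches for the best break and then treats it as fixed rejects too often.
- **Decline that slows gradually.** A line truly does not fit, so a test against a line is right to reject. Reading that rejection as a threshold is the mistake. The pilot means in section 2.0 have this shape: a fall of 15.1 − 10.8 = 4.3 points in the first six weeks and 10.8 − 8.5 = 2.3 in the next six.

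**Working it through.** **The plan's own figures.** The documents give no error rate, power or test for the segmented regression. The nearest figure is 80% power for an HRSD difference of 2.94 (SD 5.3, 13 per group, AR(1) 0.5, 10 measurements). The variance factor for a mean of 10 such measurements is 0.260, so the SD is 5.3 × √0.260 = 2.70 and the standard error is 2.70 × √(2/13) = 1.06. Then 2.94/1.06 = 2.77, and the normal approximation gives power 0.79. The figure reproduces when 5.3 is used as the SD of a single measurement.

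**Inputs from the documents**
- Visits: "Time (seven occasions), group (depressed vs. non-depressed" in section 12.0, taken as weeks 0, 2, …, 12.
- Participants: 16 depressed in POWER, 13 with complete data (section 12.0).
- Pilot means: 15.1, 10.8 and 8.5 at weeks 0, 6 and 12 (section 2.0).

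**Assumptions, because the documents are silent**
- The test and the search range for the break.
- The within-subject SD: 5.3; 5.3/√2 = 3.75 (if 5.3 is the SD of a difference of two independent scores); and 2.9 and 2.0, which have no source in the documents.
- Independent errors unless stated.

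**Models** (random intercept aᵢ)
- Line: aᵢ + b·t
- Segmented: aᵢ + b·t + d·max(t − c, 0), with c searched

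**Tests of d = 0**
- Break treated as known: t = d̂ / SE(d̂ given c = ĉ), one degree of freedom.
- 2-df likelihood ratio: LR = N·log(RSS_line/RSS_seg), N = n(7 − 1), rejected above 5.99.

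**Truths simulated**
- Straight line from 15.1 to 8.5.
- Exponential through the pilot means. Ratio per six weeks 2.3/4.3 = 0.535; amplitude 4.3/(1 − 0.535) = 9.245; floor 15.1 − 9.245 = 5.855. The mean is 5.855 + 9.245 × 0.535^(t/6).

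**Step 1: is a break always returned?** On straight-line data the segmented model fitted better than the line in every run. With the search over weeks 1-11, the 10th to 90th percentile of the estimated break was about week 1 to week 10.

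**Step 2: rejection rates with the search over weeks 2-10**

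| Truth | SD | n | Break treated as known | 2-df LR |
|---|---|---|---|---|
| Line | 3.75 | 13 | 14.8% | 5.2% |
| Line | 3.75 | 16 | 14.6% | 5.0% |
| Exponential | 5.3 | 13 | 23.0% | 10.3% |
| Exponential | 5.3 | 16 | 24.7% | 11.2% |
| Exponential | 3.75 | 13 | 30.6% | 16.0% |
| Exponential | 3.75 | 16 | 33.5% | 17.7% |
| Exponential | 2.9 | 13 | 40.0% | 22.0% |
| Exponential | 2.9 | 16 | 44.7% | 25.9% |

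Searching weeks 1-11 and extending the SD down to 2.0 gives 23-69% (break treated as known) and 10-49% (2-df) on the exponential; the line figures stay at 14-15% and about 5%. Narrowing the search to weeks 4-8 lowers the first line figure to about 10%. If errors follow AR(1) 0.5 and this is not modelled, the line figures become about 16-19% and 6-10%.

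**Step 3: does calibration alone solve it?** The LR cut-off that gives 5% on straight lines is about 6.0 with independent errors and about 7 with unmodelled AR(1) 0.5. It restores the straight-line error rate, but on the smooth curve the calibrated test still prefers a break to a line in about 10-48% of data sets (SD 5.3 to 2.9, n 13 to 32). A smooth comparator is therefore also needed. Even then AIC prefers the break to a quadratic in about 13-32% of smooth data sets.

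**Step 4: what would a strict rule cost?** With a true week-6 break to a plateau and n = 13-16, requiring the segmented model to beat both line and quadratic at 5% detects it in about 7-36%. Against the line alone, detection is 46-100%.

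**The case against.** **No test is named, so no error rate belongs to the plan.** This stands. A reader might infer that following the plan produces false thresholds at 14-15%. The documents do not support that. They treat the break as an unknown parameter of a non-linear model, and a 2-df likelihood-ratio test, or a Wald test that carries the break's uncertainty, rejects straight lines in only 3-8% with independent errors. Inflation is the result of one avoidable choice. Nor is there a single correct critical value; it moves with the search range and the error structure.

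**Rejecting a line on curved data is not a false positive.** This stands. The 23-69% and 10-49% measure how often curvature would be noticed and could be misread.

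**Individual breaks are not shown to be noise.** A reader might fit each person's seven points separately and conclude that they are. The plan intends random-effects models, which borrow strength across subjects, so separate fits test a method it does not propose. It does not say whether the break itself is random.

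**Smooth trends are planned, and the segmented model also serves estimation.** Both are true. But the quadratic is chosen by eye for another model, the polynomials are a feature of the software, and estimating a break calls for an interval. None of this supplies the missing comparison.

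**Conclusion.** The concern holds as a gap in the decision procedure. The plan poses an existence question about a threshold and specifies only a model that presupposes one. That conclusion rests on the text and needs no simulation.

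The numbers show what is at stake under stated assumptions: seven visits, 13-16 participants, a random intercept and within-subject SDs that the documents do not give. The straight-line error can be near nominal or about three times nominal (14-15% against 5%), depending on a test not yet chosen. The risk of reading gradual slowing as a threshold remains under either test.

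The threshold is part of an Aim 2 hypothesis, so this should be settled before analysis. It does not touch the primary comparison of HRSD change between POWER and control.

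**What to change.** Add a paragraph to the Data Analysis Plan in section 12.0:

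1. Fit a straight-line model with the same random effects and error structure. Compare the segmented model with it by a parametric-bootstrap test, or another test that allows for the estimated break. State the search range in advance.
2. Report a smooth fit, such as quadratic time, beside the segmented fit, with AIC for both. Describe the finding as *a threshold or gradual slowing* unless the segmented model is clearly better.
3. Report the break time with a bootstrap or profile-likelihood interval.
4. Present subject-level breaks only as random-effect estimates with their uncertainty, labelled exploratory, and say whether the break itself is a random effect.

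Do not require the segmented model to beat both comparators at 5%: real breaks would then usually be missed (Step 4 of the working).

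The cost is the paragraph, some computing time and fewer threshold claims. No data collection changes.
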